4.1. Safety Endpoints

The following safety endpoints will be assessed in Parts I and III:

- The incidence of adverse events ;
- The observed values and the changes from baseline in vital signs;
- The observed values and the changes from baseline in the Children's Depression Inventory, Second Edition, Parent and Self-Report Profiles (CDI-2);
- The observed values in the Children's Columbia-Suicide Severity Rating Scale (C-SSRS);
- The observed values in electrocardiogram (ECG) parameters and the shifts from parent study baseline for clinically significant abnormal findings;
- The observed values and the changes from baseline in clinical laboratory parameters (hematology, serum chemistry, and urinalysis).

The following safety endpoint will be assessed in Part II:

- The incidence of adverse events;
- The observed values and the changes from Week 28 (randomized withdrawal baseline) in the Children's Depression Inventory, Second Edition, Parent and Self-Report Profiles (CDI-2);
- The observed values in the Children's Columbia-Suicide Severity Rating Scale (C-SSRS);

In addition to routine monitoring of adverse events, clinical laboratory parameters, 12-lead ECGs, and safety scales, an IDMC will monitor safety during the conduct of the study.

4.2. Efficacy Endpoint

The following key efficacy endpoint will be assessed in Part II:

- The change in the TTS of the YGTSS from week 28 (randomized withdrawal baseline) to week 30 (end of randomized withdrawal).

The following exploratory efficacy endpoints will be assessed in Part II:

█ [REDACTED]

█ [REDACTED]

4.3. Exploratory Endpoints

The following exploratory endpoints will be assessed in Parts I and III at the visits in which the data is collected:

█ [REDACTED]

█ [REDACTED]
█ [REDACTED]

This document is confidential.

Statistical Analysis Plan for Interventional Studies

Sponsor: Teva Branded Pharmaceutical Products R&D, Inc./Nuvelution TS Pharma, INC.

Protocol No.: TV50717-CNS-30047

[Redacted text block containing multiple lines of blacked-out content]

This document is confidential.

5. Analysis Sets

5.1. Intent-to-Treat Analysis Set

The Intent-to-Treat (ITT) Analysis Set will include all enrolled patients into this study, regardless of whether or not a patient took any IMP.

This analysis set will be used in all study population and efficacy analyses for Parts I and III combined.

5.2. Safety Analysis Set

The Safety Analysis Set will include all patients who receive at least 1 dose of IMP.

The Safety Analysis Set will be used for all safety analyses. This analysis set will be used in all safety analyses for Parts I and III combined.

5.3. Randomized Withdrawal ITT Population

The Randomized Withdrawal ITT (RWITT) Population will include all patients that completed Part I and were randomized to Part II (Note that randomization occurs at the week 28 visit).

5.4. Randomized Withdrawal Safety Population

The Randomized Withdrawal Safety (RWSAF) Population will include all patients in the RWITT who are administered any study drug in the randomized withdrawal period.

All summaries of safety measures in Part II will be summarized descriptively in the RWSAF Population. All safety summaries based on the RWSAF will use the actual treatment patient received during the randomized drug withdrawal period.

5.5. Randomized Withdrawal Modified Intent-to-Treat Population

The Randomized Withdrawal Modified Intent-to-Treat (RWmITT) Population will include all patients in the RWITT who receive study drug in the randomized withdrawal period and have a YGTSS TTS at both the week 28 visit (randomized withdrawal baseline) and the week 30 visit (end of randomized withdrawal).

This study population will be used for sensitivity efficacy analysis in Part II. In this population, treatment will be assigned based on the treatment to which patients were randomized, regardless of which treatment they actually received.

5.6. Responder Randomized Withdrawal Modified Intent-to-Treat Population

The Responder Randomized Withdrawal mITT (RRWmITT) Population will include all patients in the RWmITT that had a $\geq 25\%$ reduction in the TTS from baseline in the parent study to week 28. This study population will be used in the primary efficacy analysis in Part II. In this population, treatment will be assigned based on the treatment to which patients were randomized, regardless of which treatment they actually received.

5.7. Protocol Deviations

Protocol deviation management at Syneos Health is detailed in Processing and Management of Protocol Deviations (3100.W02). For details on the process for defining analysis datasets refer to (Blind) Data

This document is confidential.

Statistical Analysis Plan for Interventional Studies

Sponsor: Teva Branded Pharmaceutical Products R&D, Inc./Nuvelution TS Pharma, INC.
Protocol No.: TV50717-CNS-30047

Review and Definition of Analysis Sets SOP (3911). Major protocol deviations will be summarized for Parts I and III combined, and Part II.

This document is confidential.

6. General Aspects for Statistical Analysis

6.1. General Methods

Statistical methodology and analyses are in accordance with the principles outlined by the ICH E9 guidelines. All statistical analyses will be conducted using SAS statistical software version 9.4 or above.

Tables, listings and figures (TLFs) will be produced in accordance with the principles outlined by the ICH E3 guidelines.

Data summaries will use descriptive statistics (number of patients [n], mean, standard deviation [SD], standard error [SE], median, minimum, and maximum) for continuous variables, and frequency and percentage of patients for categorical and ordinal variables, unless otherwise specified. For continuous variables, if $n < 5$ then only median, min and max will be presented.

Unless otherwise specified, all statistical tests will be two-tailed using a 0.05 level of significance. All confidence intervals (CIs) will be two sided 95% CIs.

Only visits mapped to scheduled visits will be included in by-visit summaries. All visit assessment data will be included in shift tables and will appear in the patient listings.

In general, endpoints assessed in Parts I and III will be summarized for Parts I and III combined and endpoints assessed in Part II will be summarized separately for Part II.

For assessments conducted at each visit, analyses for Parts I and III combined will include Week 28 assessment, but Week 30 assessment will not be included. Summary for Part II will include Week 28 (the randomized withdrawal baseline) and Week 30.

For analyses performed by time period, the date of Week 28 and Week 30 will be considered as the first and last day of Part II, respectively. Summary for Parts I and III combined will not include period between Week 28 assessment and Week 30 assessment, which will be covered under Part II summary.

6.2. Key Definitions

6.2.1. Baseline Values

Three baseline values will be defined:

- Parent study baseline: Parent study baseline is defined as the last non-missing measurement on or prior to the first dose of study IMP from the parent study. This baseline is used to define RRWmITT population (Section 5.6), sensitivity analysis for the TTS of the YGTSS from Week 28 to Week 30 (Section 8.2.1), and ECG analysis (Section 9.8).
- Baseline: Baseline is defined as the last non-missing measurement on or prior to the first dose of open-label IMP. In general, the Week 13 values from Study TV50717-CNS-30046 or the Week 9 values from Study TV50717-CNS-30060 will serve as baseline in this study, except for the lab assessments. For the patients rolling over from Study TV50717-CNS-30046, the Week 12 lab values will serve as the baseline in this study, or the Week 13 lab values, if the patient repeated lab assessments at Week 13. Similarly, for the patients rolling over from Study TV50717-CNS-30060, the Week 8 lab values will serve as baseline, or the Week 9 lab values if patients repeated lab assessments at Week 9. Baseline will be used for the efficacy and the safety tables for the Parts I and III combined.

This document is confidential.

- Randomized withdrawal baseline: For the patients who are randomized in Part II, the randomized withdrawal baseline is defined as the measurement at Week 28. This baseline will be used for all efficacy tables and safety tables during randomized withdrawal period.

6.2.2. First Dose Date

There are 3 first dose dates:

- The Part I first dose date will be the date that the first dose of open-label IMP is administered;
- The Part II first dose date will be the date that the first dose of the randomized, double-blind IMP is administered;
- The Part III first dose date will be the date that the first dose of the double-blind titration TEV-50717 is administered.

Dose starting and stopping dates in Parts I and III maintenance period are collected on CRF page per week per pills strength (6 mg, 9 mg, and 12 mg). They are collected per dispensed visit per bottle during Part II and Part III titration period. The Part I first dose date will be derived as the earliest dose starting date obtained from CRF. Part II first dose date will be the earliest dose starting date for any bottles dispensed on the Week 28 visit. Part III first dose date will be the earliest dose starting date for any bottles dispensed on the Week 30 visit.

6.2.3. Last Dose Date

There are 3 last dose dates that will be used for the analyses:

- The Part I last dose date will be the date of the last dose of the study IMP before the day after Week 28 visit, or the first dose of double-blind IMP if patient is dosed during randomized withdrawal period;
- The Part II last dose date will be the date of the last dose of double-blind IMP during randomized drug withdrawal period;
- The Part III last dose date will be the date of the last dose of open-label IMP during Part III.

6.2.4. Study Day

Study Day is the number of days starting from the first administration of open-label IMP, which is counted as Study Day 1. If the assessment date is after the date of the first dose of open-label IMP, the study day is calculated as date of assessment - date of the first dose of open-label IMP + 1. If the assessment date is prior to the date of the first dose of open-label IMP, the study day is calculated as date of assessment - date of the first dose of open-label IMP.

6.2.5. Duration of IMP

Duration of Part I IMP (day) = The Part I last dose date – The Part I first dose date + 1;
Duration of Part II IMP (day) = The Part II last dose date – The Part II first dose date + 1;
Duration of Part III IMP (day) = The Part III last dose date – The Part III first dose date + 1;

Duration of Part I, II, and III combined IMP will be determined as:

Duration of Part I, II, and III combined IMP (day) = Duration of Part I IMP (day) + Duration of Part II IMP (day) + Duration of Part III IMP (day).

This document is confidential.

Statistical Analysis Plan for Interventional Studies

Sponsor: Teva Branded Pharmaceutical Products R&D, Inc./Nuvelution TS Pharma, INC.
Protocol No.: TV50717-CNS-30047

Duration of Parts I and III combined IMP will be determined as:

Duration of Parts I and III combined IMP (day) = Duration of Part I IMP (day) + Duration of Part III IMP (day).

Determination of duration of IMP for any patient that does not fall into one of the categories above will be determined on a case-by-case basis in the statistical data review meeting.

6.2.6. Parts Start and End Dates

For adverse events and concomitant medication, analyses are performed by time period. The following definitions will be used:

- Part I
 - Start Date – the day of the Day 1 visit;
 - End Date - the day of the Week 28 visit, or the day before the Part II first dose date, if patient is dosed during Part II and the Part II first dose date is earlier. If a patient is enrolled but discontinues treatment before the Week 28 visit, Part I is until the last dose of study treatment.
- Part II (The randomized withdrawal period):
 - Start Date - the day after the Week 28 visit, or the Part II first dose date, if it is earlier;
 - End Date the day of the Week 30 visit. If a patient is randomized but discontinues treatment before the Week 30 visit, Part II is until the last dose of study treatment.
- Part III:
 - Start Date - the day after Week 30 visit;
 - End Date - the day of the Week 56 visit. If a patient completed Part II, but discontinues before the Week 56 visit, Part III is until the last dose of study treatment.

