Visit window (days)	±3 from week 21			±3	±3 days						±3 from week 54		
In-clinic visit	X		X		X		X	X		X	X		X
Telephone contact		X		X		X			X			X	
Evaluate/Adjust IMP			X	X	X	X							X
Informed consent/assent													
Vital signs and weight ^e	X ^f		X		X		X	X		X ^b	X		X
Physical examination	X		X							X			X ^c
Neurological examination										X			X ^g
Height	X		X		X		X	X		X	X		X ^g
12-lead ECG ^h	X									X			X ^g
Chemistry/Hematology/Urinalysis	X									X			X ^g
Urine drug screen													X ^g
β-HCG test ⁱ	X						X			X			X ^g
CDI-2 (Parent and Self-Report) ^j	X		X				X	X		X	X		X ^g
Children's C-SSRS (Baseline/Screening) ^k													
Children's C-SSRS (Since Last Visit) ^k	X		X				X	X		X	X		X ^g
YGTSS ^{l, m}	X		X				X	X		X	X ⁿ		
TS-CGI ^m	X						X	X		X	X		

This document is confidential.

Statistical Analysis Plan for Interventional Studies

Sponsor: Teva Branded Pharmaceutical Products R&D, Inc./Nuvelution TS Pharma, INC.

Protocol No.: TV50717-CNS-30047

	Part II			Part III									U
	Randomized drug withdrawal			Maintenance (resumed) or titration post-drug withdrawal			Maintenance			Follow-up			
Study week ^a	28 ^b (Day 196)	29 (Day 203)	30 (Day 210)	31 (Day 217)	32 (Day 224)	33 (Day 231)	34 (Day 238)	41 (Day 287)	47 (Day 329)	54/ET ^c (Day 378)	55 (Day 385)	56 ^d (Day 392)	
Visit window (days)	±3 from week 21			±3	±3 days						±3 from week 54		
TS-PGII ^m	X						X	X		X	X		
TS-PGIS ^m	X						X	X		X	X		
Tic-free Interval ^k	X						X	X		X	X		
CY-BOCS ^k	X						X			X	X ^o		
C&A-GTS-QOL (including VAS) ^k	X						X			X			
Contact IRT and dispense IMP and patient diary	X ^p		X ^p		X ^p		X ^q	X ^q					X ^{g, r}
Collect IMP	X		X		X		X	X		X			X ^g
Assess IMP accountability/compliance/supply	X	X ^s	X	X ^s	X	X ^s	X	X	X ^s	X			X ^g
Assess adverse events	X	X	X	X	X	X	X	X	X	X	X	X	X
Concomitant medications ^t	X	X	X	X	X	X	X	X	X	X	X	X	X

^a Assessments to occur at end of study week (±3 days).

^b At the week 28 visit, the patients will be randomized 2:1 to their current dose of TEV-50717 or placebo in order to check for return of symptoms.

^c For patients who withdraw prematurely, an early termination visit should be conducted as soon as possible after the last dose of IMP. All patients who discontinue early will have a follow-up telephone contact for safety evaluation 2 weeks after their last dose of IMP; evaluations will be as described for week 54 visit.

^d This visit is a telephone contact for safety evaluation.

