6.2.7. Periods Start and End Dates

Adverse events will also be summarized by periods below:

- Part I Titration Period
 - Start Date - the Day 1 visit;
 - End Date - the last dose of study treatment during titration period (up to and including Week 8 visit).
- Part I Maintenance Period

For patients who completed any assessments after Week 8 visit, the start and end dates are:

 - Start Date - the day after Week 8 visit;
 - End Date - the Part I last dose date .
- Part II and III Treatment Period

For patients who are randomized

 - Start Date - the start date of Part II;
 - End Date - the last dose of study treatment during the study.
- Follow-up Period
 - Start Date - the day after the last dose of study treatment;
 - End Date - the day of the last visit.

Periods are not corresponding to Parts. Events occurred after last dose of study treatment are included with each Parts, but are not included period. Events after the last dose of study treatment will all be summarized with the follow-up period.

This document is confidential.

Statistical Analysis Plan for Interventional Studies

Sponsor: Teva Branded Pharmaceutical Products R&D, Inc./Nuvelution TS Pharma, INC.
 Protocol No.: TV50717-CNS-30047

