- Parts I and III combined, based on the Safety Analysis Set. The events that occurred in Part II will not be included. Table will contain one overall column. All tables will include number, frequency of patients with the event, and EAIR. All AE tables will be prepared for Part I and III combined.

This document is confidential.

Statistical Analysis Plan for Interventional Studies

Sponsor: Teva Branded Pharmaceutical Products R&D, Inc./Nuvelution TS Pharma, INC.
Protocol No.: TV50717-CNS-30047

- Part II is based on the RWSAF population and presented by the actual treatment received during the randomized withdrawal period. Table will include number and frequency of patients with the event. All AE tables will be prepared for Part II.
- Parts I, II, and III combined, based on the Safety Analysis Set. Table will contain one overall column. The Parts I, II, and III combined tables will be presented for entire study and by each Part. All tables will include number, frequency, and the EAIR. The overview of AEs, AEs by SOC and preferred terms, and the SMQ summaries will be presented for Parts I, II, and III combined.
- Periods, based on the Safety Analysis Set. Table will contain one overall column. All tables will include number, frequency, and the EAIR. The overview of AEs and AEs by SOC and preferred terms will be presented by periods.

For summary of patient, the following rules will apply:

1. Patients having more than 1 event with the same PT will be counted once for that term.
2. Patients having more than 1 event with the same SOC will be counted once for each event and once for that SOC.
3. For tabulations by severity, only a patient's most severe event within the category (e.g. overall, SOC, PT) will be counted; similarly, for tabulations by relationship, only a patient's most related event within a category will be counted. The denominator for percentages will be the number of patients in Safety Analysis Set for the given treatment group or overall (i.e., the N's for the columns).

For the summary of incidence rate, all events will be included.

Listings will be provided for all AEs and the following subsets:

- All TEAEs
- Serious TEAEs
- TEAEs leading to study drug discontinuation
- TEAEs leading to dose interruption
- TEAEs leading to dose reduction
- TEAEs leading to death.

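### Section 6.2.6 ends a discontinuer's Part at the last dose but runs a completer's Part III to Week 56, contradicting Section 6.2.7 and removing post-dose AEs from Part-based safety tables

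*SAP*

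**What the plan says.** Section 6.2.6 sets the Part dates used for adverse events and concomitant medication. It has one stopping rule for each Part:

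- Part I: "If a patient is enrolled but discontinues treatment before the Week 28 visit, Part I is until the last dose of study treatment".
- Part II: "If a patient is randomized but discontinues treatment before the Week 30 visit, Part II is until the last dose of study treatment".
- Part III, completers: "End Date - the day of the Week 56 visit".
- Part III, discontinuers: "If a patient completed Part II, but discontinues before the Week 56 visit, Part III is until the last dose of study treatment".

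Section 6.2.7, which defines the Periods, closes with a note on how the two systems differ: "Events occurred after last dose of study treatment are included with each Parts, but are not included period". It then sends all post-dose events to the Follow-up Period.

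Table 3 (continued), footnote c, in Section 3.8 provides for data after stopping: "All patients who discontinue early will have a follow-up telephone contact for safety evaluation 2 weeks after their last dose of IMP". Section 9.4 collects AEs to the end of follow-up and puts no upper time limit on the TEAE definition. It refers to Section 6.2.6 for allocation to Parts and to Section 6.2.7 for allocation to Periods. All AE tables are produced for Parts I and III combined and for Part II. For Periods the set is smaller: "The overview of AEs and AEs by SOC and preferred terms will be presented by periods".

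On the start of Part II, Section 6.1 says that for analyses by time period "the date of Week 28 and Week 30 will be considered as the first and last day of Part II, respectively". Section 6.2.6 starts Part II the day after the Week 28 visit, or at the first blinded dose if that is earlier.

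**The concern.** Two adjacent sections give opposite answers to one question: does an event that starts after the last dose belong to a Part? The rule that Section 9.4 points to is the one that excludes such events, and it does so only for patients who stopped early. Completers have their off-drug follow-up counted in Part III.

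Safety and tolerability is the primary objective, and the Part-based tables carry most of its detail: severity, relationship, serious events by SOC/PT and the SMQs for suicide/self-injury, depression and Parkinson-like events. Whether a patient's off-drug events reach those tables should not depend on whether the patient finished the study. The Part I interim presents safety in the same way as Section 9, so the question arises there too.

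**Working it through.** The SAP gives no figure for this point, so there is nothing to reproduce. The check is on dates.

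**Inputs.** Planned dosing lasts up to 54 weeks (Section 3.7). Table 3 gives Week 54 = Day 378, Week 30 = Day 210 and Week 56 = Day 392. The safety contact for a discontinuer is 2 weeks after the last dose (footnote c).

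**Step 1: post-dose days inside a Part.** Use Part end minus last dose.

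| Patient | Last dose | AEs collected to | Part ends (6.2.6) | Post-dose days in a Part | Collected days in no Part |
|---|---|---|---|---|---|
| Completer | 378 | 392 | 392 | 392 − 378 = 14 | 0 |
| Stops in Part I | 100 | 114 | 100 | 0 | 14 |
| Stops in Part II | 203 | 217 | 203 | 0 | 14 |
| Stops in Part III | 300 | 314 | 300 | 0 | 14 |

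The stopping days 100, 203 and 300 are illustrations; the result is the same for any stopping day. Under Section 6.2.7 the last column would be 0 for everyone.

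**Step 2: which tables lose the events if Section 6.2.6 is followed.**

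| Output | Post-dose TEAE of a discontinuer |
|---|---|
| Severity, relationship, serious by SOC/PT (Parts I and III combined; Part II) | lost |
| SMQ summaries for Parts I and III combined, Part II and each single Part | lost |
| Entire-study column for Parts I, II and III combined | not stated |
| Follow-up Period overview (includes serious, related and fatal totals) and SOC/PT table | kept |
| Listings | kept |

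**Step 3: follow-up time involved.** Each discontinuer contributes 14 / 365.25 = 0.038 patient-years. The SAP gives no discontinuation rate for this study, so 20% to 40% is an assumption.

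- Planned 226 (Table 2): 45 to 90 patients. 45 × 14 / 365.25 = 1.7 and 90 × 14 / 365.25 = 3.5 patient-years.
- The 157 enrolled at 09Aug2019 (Table 2): 31 to 63 patients. 31 × 14 / 365.25 = 1.2 and 63 × 14 / 365.25 = 2.4 patient-years.

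No AE rate is given, so no event count follows.

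**Step 4: Part II needs its own window.** A Part II completer's window closes at Week 30 (Day 210), with no off-drug tail. For a patient whose last dose is Day 203, a full 14-day extension would run to Day 217, which is 217 − 210 = 7 days longer than a completer is observed. Closing at Day 203 is 7 days shorter. Only closing at the planned Week 30 date makes the two equal.

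**Step 5: rate denominator.** Section 6.2.8 divides by patient-years of treatment. A completer's Week 55 and 56 events already enter the Part III numerator with no matching exposure, and the section is silent on this.

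**Step 6: Part II start.** Under Section 6.1 Day 196 belongs to Part II. Under Section 6.2.6 it belongs to Part I unless blinded dosing began by then. Table 3 (continued), footnote p, has blinded dosing start on Day 197. Under Section 6.1, an AE on Day 196 could be charged to a randomized arm before any blinded dose.

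**The case against.** The strongest reply is that Section 6.2.7 states the intent, and a programmer who follows it loses nothing. That is right as far as it goes: the loss depends on which section is followed. But Section 9.4 names Section 6.2.6 for Parts, so exclusion is the more direct reading, and both rules cannot be programmed.

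Several stronger conclusions are tempting and do not hold:

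- *The events that made patients stop are removed.* An AE leading to dose reduction, interruption or discontinuation normally begins by the last dose, so it stays in the Part. The SAP gives no reasons for discontinuation in this study.
- *A post-dose suicidality or depression event appears in no SMQ table.* Section 9.4 also plans an entire-study SMQ summary and does not say whether events outside every Part count in it. Only the by-Part loss is established.
- *Safety rates are biased downward in general.* The exposure-adjusted rate uses treatment time only, so stopping the numerator at last dose agrees with that denominator. The completers' tail is what departs from it. What is shown is unequal counting and missing detail, not a general bias.
- *The events vanish.* They remain in the listings and the Follow-up tables, including serious, related and fatal totals.

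Ending Part III at last dose for everyone would also remove the asymmetry. It would contradict Section 6.2.7 and take collected safety data out of the detailed tables, so it is the weaker choice. The Part II start mismatch is only one day, and Section 6.2.6 is the AE-specific rule; it still needs aligning.

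**Conclusion.** The point holds as an error in a stated rule. Section 6.2.6 contradicts Section 6.2.7 and treats discontinuers and completers unequally: 0 against about 14 post-dose days inside a Part. If Section 9.4's reference to Section 6.2.6 is followed, discontinuers' post-dose TEAEs drop out of the Part-based severity, relationship, serious-by-SOC/PT and by-Part SMQ tables. The 14 days assume nominal visit timing and dosing to Week 54. The 1.2 to 3.5 patient-years rest on an assumed 20% to 40% stopping early and on 157 or 226 enrolled; the number of events cannot be derived from the SAP. The defect does not depend on that number, because the primary-objective tables cannot be programmed from two conflicting rules.

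**What to change.** 1. In Section 6.2.6, for AE allocation, replace the three clauses that end a discontinuer's Part at the last dose. Count post-dose events through last contact, up to last dose + 14 days, in the Part in which treatment stopped, as Section 6.2.7 states.
2. In Section 9.4, state that the entire-study column for Parts I, II and III combined includes these events, SMQ summaries included.
3. For the by-arm Part II tables, cap the window at the planned Week 30 date so that discontinuers and completers are observed for the same time. Show later events in the combined and Follow-up tables.
4. In Section 6.2.8, state how post-dose events enter the exposure-adjusted rate, for completers and discontinuers alike, given that the denominator is treatment exposure only.
5. Align the Part II start day in Section 6.1 with Section 6.2.6.

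The cost is SAP wording and one date derivation. The data are already collected. Reported AE counts may rise slightly. The change should be made before database lock, so that the choice between the two rules is not made with treatment codes known.
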